14.6. Secondary Analysis

Not applicable.

14.7. Exploratory Analysis

The exploratory analyses will be conducted on the Intention-to-Treat population.

The following endpoints will be collected and analyzed separately for each timepoint:

- 1. Commitment to lens wear: Do you want to continue to wear contact lenses after this study?
- 2. Reasons for Discontinuation (if applicable): Which of the following is the main reason why you want to stop wearing contact lenses?
- 3. Insertion Time OU (at the initial fitting, after approximately 1-week of wear, and after approximately 2-weeks of wear).
- 4. Removal time OU (at the initial fitting, after approximately 1-week of wear, and after approximately 2-weeks of wear).
- Confidence (baseline, post fitting, after approximately 1-week of wear, and after approximately 2-weeks of wear).
- 6. Motivation (baseline, post fitting, after approximately 1-week of wear, and after approximately 2-weeks of wear).
- 7. Lens performance (CLUE vision, comfort, and handling scores) at fitting, after approximately 1-week of wear, and after approximately 2-weeks of wear.

In addition, the relationship between endpoints (i.e., CLUE[™] scores, insertion time (OU), and removal time (OU) and human factors will also be investigated both graphically (e.g., via scatterplots) and through a correlation analysis, at fitting and 1-week follow-up.

Anatomical human factors will include palpebral aperture height (PAH), horizontal visible iris diameter (HVID), hand length, palm width, hand dominance and while non-anatomical human factors will include motivation, confidence, and demographics (e.g., gender, age).

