1.5. Relevant Literature References and Prior Clinical Data Relevant to Proposed Clinical Study

Recent review of the literature points to several factors that may contribute to new wearer dropout. Sulley *et al* found that the main reasons for discontinuation were problems with vision (41%), discomfort (36%), and handling problems $(25\%)^4$.

This study will measure commitment to lens wear in a healthy neophyte population. Eligible subjects will be trained and fitted into a commercially available daily disposable contact lens brand (AO1D), known for its acceptable clinical performance. After approximately two weeks of wear experience, subjects will be interviewed about their commitment to lens wear. Subjects may drop out of the study prematurely, and if so, the reason for dropping out will be documented.

For the most comprehensive information regarding study lenses refer to the package insert of the marketed product (Appendix C).

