2. STUDY OBJECTIVES, ENDPOINTS AND HYPOTHESES

2.1. Objectives

Primary Objective: The primary objective of this study is to estimate the incidence rate (percentage) of eyes with clinically significant slit-lamp findings (Grade 3 or 4) related to the study lens after approximately 2-weeks of lens wear.

Exploratory Objectives: The other objectives are to measure commitment to lens wear in neophyte subjects after approximately two weeks of wearing experience, measure Insertion & Removal (I&R) skills, evaluate new wearer confidence and motivation for lens wear, and assess lens performance (CLUE vision, comfort & handling scores).

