7. STUDY EVALUATIONS

7.1. Time and Event Schedule

Table 3: Time and Events

Visit Information	Visit 1 Screening, Baseline, Treatment 1	Visit 2 Treatment 1 Follow- up 1	Visit 3 Treatment 1 Follow- up 2
Time Point	Day 0	7 ± 1 day following Visit 1	7 ± 1 day following Visit 2
Estimated Visit Duration	4 hours	2 hours	2 hours
Statement of Informed Consent	X		
Children's Assent (if applicable)	x		1
Parent or Legal Guardian Statement of Informed Consent (if applicable)	x		
Demographics	X		
Medical History/Concomitant Medications	X	X	X
Eligibility Following Screening	X		
Confidence & Motivation Questionnaire	X	X	x
Entrance Visual Acuity	X	X	X
Palpebral aperture height (PAH)	X		
Horizontal Visible Iris Diameter (HVID)	x		
Hand dominance	x		
Hand size (Hand length, palm width)	x		
Subjective Sphero-Cylindrical Refraction and best-corrected VA	x		Х
Slit Lamp Biomicroscopy	X	X	x
Eligibility Following Baseline Evaluation	x		
Lens Selection	x		
Lens Insertion & Removal Training	x		
Lens Insertion & Removal (timed)	x	х	Х
I&R learning session (timed)	x		
Over Refraction and Visual Acuity (if necessary)	X	X	
Lens Power Modification (if applicable)	X	х	
Subject Reported Ocular Symptoms	x	x	Х
Post Fit Questionnaires	X		
General Fit Assessment	x	X	X
Exit Snellen Distance Visual Acuity	x	x	х
Dispense Patient Instruction Guide (New wearer contact lens education)	х		
Dispense Test Article	X	X	
Lens wear time		X	X
Follow-up Questionnaire		X	x

Visit Information	Visit 1 Screening, Baseline, Treatment 1	Visit 2 Treatment 1 Follow- up 1	Visit 3 Treatment 1 Follow- up 2
Time Point	Day 0	7 ± 1 day following Visit 1	7 ± 1 day following Visit 2
Estimated Visit Duration	4 hours	2 hours	2 hours
Commitment to Lens wear (Exit Interview)			x (at Exit Evaluation)
Study Completion			X

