1.21	Patient Instruction Guide (PIG)	Record in EDC that the subject was instructed on proper use and care of contact lenses and provided a copy of the Patient Instruction Guide. Encourage the subject to ask questions and clarify information, if necessary.		
1.22	Lens Selection	Provide the subject a new pair of contact lenses.		
1.23	Lens Insertion	The subject or the Investigator will insert the study lenses. Check for lens damage under the slit lamp before		

CL	December	Visit 1: Treatment 1 Lens Fitting
Step	Procedure	Details
1.24	Lens Settling	Replace damaged lenses if necessary. Allow the study lenses to settle for a minimum of 10 minutes.
		The subject will spend this time experiencing vision. Instruct the subject to look at distance objects, near objects, and experience bright & dim lighting conditions.
1.25	Subjective Best Sphere Over Refraction	Perform the monocular subjective best sphere refraction over the study lenses with a phoropter, trial lenses, or flipper bars (adopt the maximum plus to maximum visual acuity). Record distance visual acuity to the nearest letter (OD and OS).
1.26	Lens Power Modification (if applicable)	Adjust the lens power if the subject's best sphere over-refraction is not Plano. For each power modification, select the adjusted fitting lens power as appropriate and repeat steps 1.23 through 1.26.
1.27	Subject Reported Ocular Symptoms	Up to two power modifications are allowed. Subjects will respond to a verbal open-ended symptoms questionnaire.
1.28	General Lens Fit Assessment	Evaluate lens centration, movement on blink, and push-up test for each eye. An unacceptable fit is deemed by one of the following criteria: Iimbal exposure at primary gaze or with extreme eye movement. edge lift. excessive movement in primary and up gaze. insufficient movement in all three of the following conditions: primary gaze, up gaze, and push-up test.
1.29	Confidence & Motivation Questionnaire	Note: If lens fit is unacceptable for either eye, the subject will be discontinued from the study. The subject will complete the Confidence & Motivation Questionnaires directly.
1.30	Post-Fit Questionnaire	The subject will complete the Post-Fit Questionnaire directly.
1.31	Exit VA	Record the subject's distance visual acuity, OD and OS, to the nearest letter.

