1.32	Continuance	For the subject to continue in the study, they must meet all three of the following criteria: • Visual acuity is 20/30 or better OD and OS. • The lens fit is acceptable OD and OS. • Investigator approval.

04-	Visit 1: Treatment 1 Lens Fitting			
Step	Procedure	Details If the Investigator does not approve the dispensing of the first study lens, then the study is terminated for that subject.		
1.33	Dispense	that subject. The lenses will be dispensed for a 6-8 day wearing period. Subjects will be encouraged to wear the study lenses every day, building up the wearing time if necessary. The lenses will be worn in a daily wear, daily disposable modality. Rewetting drops are permitted if needed. The subject should only use the sponsor supplied lens care products. (Section 6.1) Supply the subject a bottle of contact lens solution or saline for rinsing purposes, if necessary. Instruct subjects to return any unworn lenses to the clinical site. Subjects will be scheduled for their 1-week follow-up visit, ensuring that they wear the study lens to the follow-up visit. Note: Dispense the subject enough lenses to last them to their next scheduled visit, plus an extra pair. If the subject requires additional replacement lenses, instruct them to contact the clinical site for replacement. As much as reasonably possible, any damaged lens and packaging should be returned to the clinical site (wet, if possible) and then returned to the Sponsor. If lens damage is present, complete the Product Quality Complaint Form. If the PQC is due to foreign matter in the packaging, to the extent possible, this foreign matter must also be returned. The lens will be stored in labeled vial with saline, and clearly differentiated from the other worn lenses that will be shipped back to the Sponsor.		
1.34	Schedule next visit	The subject may continue to wear their habitual correction (spectacles) when not wearing study contact lenses. Schedule the follow-up visit to occur in 7 ± 1 days (counting the day of this visit as day 0, the subject may return on day 6 through 8). Ensure the subject is instructed to wear the study lenses to the follow-up visit. Remind the subject to bring their spectacle		

VISIT 2

The subjects must present to Visit 2 wearing the study lenses. If the subject wishes to stop wearing contact lenses (discontinue), proceed to the Final evaluation.

		Visit 2: Treatment 1 Follow-Up 1	- 39
Step	Procedure	Details	

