3.14	Slit Lamp Biomicroscopy	FDA Slit Lamp Classification Scale will be used to grade the findings. If the subject has a Grade 3 slit lamp finding, it will be recorded as an Adverse Event and the subject will be monitored as per the guidelines given in section 13. If the clearance of the fluorescein needs to be expedited, preservative-free rewetting drops may be instilled.	

FINAL EVALUATION

The final evaluation will ordinarily take place immediately following the last scheduled follow-up visit per the study protocol. It may also take place at any point the subject discontinues the study or is terminated from the study.

Final Evaluation			
Step	Procedure	Details	1/-
F.1	Commitment to Lens Wear Questionnaire	The subject will complete the commitment to lens wear Questionnaire directly.	
F.2	Final Exam Form	Indicate if the subject completed the study successfully. If subject discontinued from the study, indicate the reason.	
F.3	Exit Refraction	Perform bare-eye subjective spherocylindrical refraction with a phoropter and record the best-corrected distance visual acuity (OD and OS) to the nearest letter.	

	Final Evaluation		
Step	Procedure	Details	
		NOTE: This step is not necessary if the subject was exited due to screen failure.	
F.4	Exit Slit Lamp Biomicroscopy (for subjects that are discontinued early)	FDA Slit Lamp Classification Scale will be used to grade the findings. If the clearance of the fluorescein needs to be expedited, preservative-free rewetting drops or saline may be instilled. This step is not necessary if the subject was exited due to screen failure. NOTE: This step is not necessary if the subject was	
		exited due to screen failure, or if biomicroscopy was performed as part of the final follow-up visit procedures (i.e., immediately prior to the final evaluation).	

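### Does the two-week commitment rate mix answers given after about zero, one and two weeks of wear?

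*Combined protocol and SAP*

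**What the plan says.** **Intended timing.** The exploratory objective in section 2.1 is to "measure commitment to lens wear in neophyte subjects after approximately two weeks of wearing experience". Section 1.5 agrees: "After approximately two weeks of wear experience, subjects will be interviewed about their commitment to lens wear". In Table 3 (section 7.1) the row "Commitment to Lens wear (Exit Interview)" has one mark, in the Visit 3 column, tied to the exit evaluation.

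**Collection.** Step F.1 of the Final Evaluation (section 7.2) reads "The subject will complete the commitment to lens wear Questionnaire directly". That evaluation normally follows Visit 3, but "It may also take place at any point the subject discontinues the study or is terminated from the study". Section 8.2 requires it for discontinued subjects. Two early routes to it are explicit:
- At Visit 1, step 1.28: "If lens fit is unacceptable for either eye, the subject will be discontinued from the study".
- At Visit 2: "If the subject wishes to stop wearing contact lenses (discontinue), proceed to the Final evaluation".

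**Analysis.** Section 14.7 opens its list with "The following endpoints will be collected and analyzed separately for each timepoint". Items 3 to 7 each carry timepoints. Item 1 (commitment) and item 2 (reason for stopping) carry none, and neither do their definitions in section 2.2. The set is the intention-to-treat population. Section 14.9 rules out imputation and promises counts of missing values. Section 14.1 keeps unscheduled visits out of the statistical analysis. Sections 2.3 and 14.4 plan no hypothesis test.

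**The concern.** Each subject answers the commitment question once, on one form. A subject who leaves at the fitting has had no dispensed wear. One who stops at Visit 2 has had about a week, and one who reaches Visit 3 about two. If all three go into one percentage, the result is not the two-week quantity of section 2.1. The missing-value count would not reveal this, because the early leavers did answer. Restricting to Visit 3, on the other hand, drops the early quitters who prompt the discussion of new-wearer dropout in section 1.5.

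The stake is the meaning of one descriptive figure. It is not a trivial one, since sections 1.5 and 4.2 present commitment as something the design is meant to measure.

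**Working it through.** **Inputs from the protocol.** About 40 enrolled and about 30 completing (sections 4.3 and 14.2). These figures fit each other and the site plan: 40 − 30 = 10 non-completers, 10/40 = 25%, 30/(1 − 0.25) = 40, and 5 sites × 8 subjects = 40. The sample size is not based on a commitment rate, and no such rate is given. With two windows of 7 ± 1 days, Visit 3 falls 6 + 6 = 12 to 8 + 8 = 16 days after lenses are dispensed, so answers at Visit 3 do meet the two-week description.

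**Assumptions.** Let E be the number of early leavers who wore a lens and answer F.1, and Y the number of Yes answers among 30 completers. Neither is in the documents.

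**If the answers were combined.** Rate = (Y + Yes answers among the E)/(30 + E). The range runs from all early leavers saying No to all saying Yes.

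| E | Y = 27 (90.0%) | Y = 24 (80.0%) | Y = 18 (60.0%) |
|---|---|---|---|
| 0 | 90.0% | 80.0% | 60.0% |
| 2 | 27/32 to 29/32 = 84.4% to 90.6% | 24/32 to 26/32 = 75.0% to 81.3% | 18/32 to 20/32 = 56.3% to 62.5% |
| 5 | 27/35 to 32/35 = 77.1% to 91.4% | 24/35 to 29/35 = 68.6% to 82.9% | 18/35 to 23/35 = 51.4% to 65.7% |
| 10 | 27/40 to 37/40 = 67.5% to 92.5% | 24/40 to 34/40 = 60.0% to 85.0% | 18/40 to 28/40 = 45.0% to 70.0% |

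**In reverse.** Suppose a combined table shows 27 Yes and 8 No with E = 5. If no early leaver said Yes, the two-week rate is 27/30 = 90.0%. If all five did, it is 22/30 = 73.3%. The width is E/30: 16.7 points for E = 5, 2/30 = 6.7 for E = 2, and zero for E = 0.

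**Why these are outer bounds.**
- Enrolment is counted from signed consent (section 4.3), so the ten non-completers include screen failures.
- Subjects lost to follow-up may never answer F.1.
- A subject discontinued at Visit 3 for unacceptable fit (step 3.8) is a non-completer under section 8.1, yet answers after about two weeks.
- The all-Yes end is implausible for subjects who leave because they want to stop wearing lenses. It suits only exits for fit, vision, compliance or similar reasons.
- The ceiling of 10 assumes that enrolment stops at 40, although sections 4.3 and 8.2 allow replacements.

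**A yardstick.** The exact 95% interval for 24/30 is 61.4% to 92.3%, which is 30.9 points wide. The plan calls for no interval; this only shows how coarse any rate from 30 subjects is.

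**Does the plan combine the answers?** Sections 1.5 and 2.1 fix the timing at about two weeks, Table 3 places the item at Visit 3, and section 14.7 asks for results by timepoint. No sentence directs one rate over all exits, and no table layout is given. The text is silent on how early-exit answers are handled.

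**The case for a change.** The best argument for a change is that silence has a likely default. With one answer per subject, no timepoint named and an intention-to-treat set not limited to completers, the section 14.7 lead-in gives a programmer nothing to split on. A single mixed rate is then the easiest output. Section 14.1 adds doubt, because an exit at an unscheduled visit might be left out while an exit at Visit 2 is kept.

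Much of this stands. The silence is real, it extends to item 2, and no other section fills it. It does not establish that a stated rule produces a wrong number: the same passages support a Visit 3 figure at least as well. The information needed to separate the answers is already collected. Step F.2 records completion status and the reason for leaving, and visit dates are kept.

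Two related points carry little weight here. The moment at which a subject counts as assigned (section 14.3) is undefined in this single-arm study, but that is a separate wording matter, and moving this one endpoint to the Safety population would be a preference. F.1 lacks the screen-failure note found in F.3 and F.4, but nothing suggests that screen failures would enter the rate.

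**Conclusion.** No change is called for. The protocol leaves open whether early-exit answers enter the two-week commitment rate. It does not instruct anyone to combine them. A sensible analyst would report Visit 3 answers, including those from subjects discontinued at that visit, as the two-week figure with its denominator, and list early-exit answers by visit of exit. No new data are needed.

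The possible effect is zero if no early leaver answers. Otherwise the ambiguity is at most E/30, for example 6.7 points for two and 16.7 for five, on the assumptions of 30 completers who all answer and early leavers who could answer either way. The primary slit-lamp endpoint is untouched, and no error rate or power is affected because nothing is tested.

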4.3. Enrollment Target and Study Duration

This study will have an enrollment target of approximately 40 subjects, and it is estimated that approximately 30 subjects will complete the study. The study will be conducted at up to 5 clinical sites, where the enrollment target for each site will be approximately 8 subjects. A subject will be considered enrolled upon signing of the informed consent/assent form.

The study enrollment period is approximately 8 weeks. Once enrolled, subjects will be in the study for about 2 weeks, making the total study duration about 10 weeks from the first subject first visit (FSFV) to last subject last visit (LSLV). Subjects who are discontinued prior to the final evaluation may be replaced at the discretion of the study sponsor. The investigation will end at the time that the study data is hard locked.

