14. STATISTICAL METHODS

14.1. General Considerations

Statistical analysis will be undertaken by the study biostatistician. A general description of the statistical methods to be implemented in this clinical trial is outlined below.

All data summaries and statistical analyses will be performed using the SAS software Version 9.4 or higher (SAS Institute, Cary, NC⁶. Throughout the analysis of data, the results for each subject/eye will be used when available for summarization and statistical analysis. Unscheduled visits will be summarized separately and will be excluded from the statistical analysis.

Summary tables (descriptive statistics and/or frequency tables) will be provided for all baseline variables, efficacy variables, and safety variables as appropriate. Continuous variables will be summarized with descriptive statistics

(n, mean, standard deviation [SD], median, minimum and maximum). Frequency count and percentage of subjects or eyes within each category will be provided for categorical data.

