14.3. Analysis Populations

Safety Population:

All subjects who were administered any test article.

Per-Protocol Population:

All subjects who successfully complete all visits and do not substantially deviate from the protocol as determined by the trial cohort review committee prior to database hard lock. Justification for the exclusion of subjects with protocol deviations from the per-protocol population set will be documented in a memo to file.

Intent-to-Treat (ITT) Population:

Intention-to-treat population will include all assigned subjects.

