14.9. Procedure for Handling Missing Data and Drop-Outs

Missing or spurious values will not be imputed. The count of missing values will be included in the summary tables and listings.

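### Section 14.7 summarises repeated measures visit by visit on whoever is present, so selective dropout can look like improvement; it also leaves open which Visit 1 confidence answer is correlated with fitting times

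*Combined protocol and SAP*

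**What the plan says.** Section 14.7 introduces the exploratory endpoints with: "The following endpoints will be collected and analyzed separately for each timepoint". Insertion time, removal time and CLUE are taken at fitting, 1 week and 2 weeks. Confidence and motivation are taken at baseline, post fitting, 1 week and 2 weeks. No change between visits is planned.

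The population is stated as: "The exploratory analyses will be conducted on the Intention-to-Treat population". Section 14.3 defines it: "Intention-to-treat population will include all assigned subjects". That does not settle who contributes at a given visit. Section 14.1 does: "the results for each subject/eye will be used when available for summarization and statistical analysis". Section 14.9 adds: "Missing or spurious values will not be imputed. The count of missing values will be included in the summary tables and listings". Each visit's summary therefore rests on the subjects who have a value at that visit.

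On numbers, section 4.3 sets a target of about 40 enrolled, and "it is estimated that approximately 30 subjects will complete the study". The same section counts a subject as enrolled on signing consent or assent.

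Section 14.7 also plans correlations of CLUE scores and insertion and removal times with human factors, at fitting and at 1 week, where "non-anatomical human factors will include motivation, confidence, and demographics (e.g., gender, age". It does not name the assessment occasion for confidence and motivation. In section 7.2 that questionnaire is given twice at Visit 1: at step 1.6, and again at step 1.29 ("The subject will complete the Confidence & Motivation Questionnaires directly"). The timed insertion and removal is step 1.18, between the two.

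**The concern.** A reader given three mean insertion times in visit order will compare them. As planned, the difference between two of them mixes two things: how the same people changed, and who was no longer there. The tables cannot separate the two.

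Selective loss is plausible in this population. Section 1.5 cites a study of new-wearer retention in which the main reasons for stopping were vision (41%), discomfort (36%) and handling (25%). Those match the three CLUE domains collected here, and handling bears on insertion and removal. The protocol's own list of reasons for stopping includes difficulty putting lenses on and taking them off. Section 8.2 withdraws subjects not successfully dispensed because of poor vision, comfort or fit.

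The secondary matter is order. The confidence item asks about ability to put lenses on. Answered after the timed session, it may partly reflect the performance just timed. A correlation with fitting time would then be hard to read as a link between a wearer's prior confidence and skill.

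**Working it through.** **1. Size of the selection effect**

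The plan has no powered sample size to reproduce. Section 14.2 rests on feasibility, and 5 sites × about 8 subjects = 40 agrees with the stated target. The implied overall loss is 1 − 30/40 = 25%, counted from consent.

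Inputs from the documents: 40 enrolled, 30 completing. Assumptions, none of which the documents give:
- Times are log-normal with SD of log σ = 0.6.
- No learning: each subject has the same time at both visits.
- A latent dropout propensity has correlation ρ with log time, and the 30 subjects least prone to leave remain.
- The number with a fitting time, n₀, is 33, 35 or 40. Only 40 is a documented figure, and it is an upper bound because it includes screen failures.

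With p = 30/n₀ retained and c = Φ⁻¹(p), the large-sample ratio of the retained mean to the full mean is

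Φ(c − ρσ) / p.

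- n₀ = 40, ρ = 0.3: c = 0.6745; Φ(0.6745 − 0.18) / 0.75 = 0.6895 / 0.75 = 0.919, a fall of 8.1%.
- n₀ = 40, ρ = 1: Φ(0.0745) / 0.75 = 0.5297 / 0.75 = 0.706, a fall of 29.4%.
- n₀ = 33, ρ = 0.3: c = 1.3352; Φ(1.1552) / 0.9091 = 0.8760 / 0.9091 = 0.964, a fall of 3.6%.
- n₀ = 33, ρ = 1: Φ(0.7352) / 0.9091 = 0.7689 / 0.9091 = 0.846, a fall of 15.4%.

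Simulation at the actual sample sizes (20,000 runs) gives slightly smaller falls, as expected with few subjects:

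| Fitted → remaining | ρ = 0 | 0.3 | 0.5 | 0.7 | 1 | Paired change |
|---|---|---|---|---|---|---|
| 33 → 30 | 0 | −3.4% | −6.1% | −9.2% | −14.4% | 0 |
| 35 → 30 | 0 | −4.9% | −8.7% | −12.8% | −19.7% | 0 |
| 40 → 30 | 0 | −7.7% | −13.4% | −19.3% | −28.5% | 0 |

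Medians do not escape. If the slowest quarter leaves, the new median is the former 37.5th percentile: exp(0.6 × −0.3186) − 1 = −17%.

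**2. Order of questionnaire and endpoint**

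I take CLUE to be carried by the Post-Fit and Follow-Up Questionnaires; the questionnaire appendix is not legible in the public copy.

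| Visit | Confidence/motivation | Timed task | CLUE |
|---|---|---|---|
| 1 | 1.6 (baseline) and 1.29 (post fitting) | 1.18 | 1.30 |
| 2 | 2.5 | 2.11 removal, 2.13 insertion | 2.6 |

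At Visit 2 the same-visit answer precedes every endpoint. At Visit 1 the post-fitting answer precedes CLUE but follows the timed task. The order is therefore in doubt only for insertion and removal times at fitting.

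**The case against.** The strongest reply is that the plan claims nothing about learning. Section 2.3 says all endpoints are summarised descriptively, section 14.4 plans no testing, and section 2.1 speaks of measuring skills and evaluating confidence. Section 14.1 shows n and median with each mean, and section 14.9 tabulates missing counts, so a shrinking denominator is visible. This stands as far as it goes: the point concerns a likely misreading, not a faulty test. But a missing count shows that subjects left without showing what their leaving did to the mean, and a within-subject change is just as descriptive.

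The second reply concerns size, and it stands. A reader might infer that 25% of fitted subjects will be lost. The documents do not support that: the fall from 40 to 30 starts at consent and so takes in failures at steps 1.5 and 1.14, who never have an insertion time. Subjects who end the learning session early may have no complete time either. Nor do the documents quantify any link between dropout and speed.

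A reader might also infer that the correlation at fitting definitely uses the post-task answer, so that the plan reverses cause and effect. Section 14.7 does not say so. It lists baseline and post fitting as separate occasions, which makes the post-fitting answer the natural reading of a correlation at fitting, but the baseline answer is collected and could be used. A correlation also asserts no direction, and section 14.7 speaks only of a relationship.

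**Conclusion.** The main point holds as a free improvement to exploratory reporting. By-visit summaries on available subjects compare different groups, and with no true change the mean time can appear to fall by about 3-14% (33 to 30 subjects) or, as an upper bound, 8-29% (40 to 30). These ranges rest on the assumed log-SD of 0.6 and a dropout-speed correlation of 0.3 to 1; with no correlation the fall is 0. The figures are for times. The same mechanism applies to CLUE, confidence and motivation, but no size was computed for them.

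The paired change of 0 follows from giving each subject the same time at both visits. Real times vary within a subject, and a paired change describes those who stayed, not all who were fitted. It removes the change in composition, not every effect of dropout.

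The secondary point is an unspecified occasion, limited to insertion and removal times at fitting. The primary endpoint, the sample size and the error rates are untouched.

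**What to change.** In section 14.7:

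1. Beside the by-visit tables, report within-subject change from the first measurement in subjects with both values, stating the number of pairs: ratio for insertion and removal times and difference for CLUE, each with a 95% confidence interval; shift tables for confidence and motivation. The intervals are descriptive and fit sections 2.3 and 14.4.
2. Name the baseline confidence and motivation answer (step 1.6) as the factor correlated with insertion and removal times at fitting. Leave fitting CLUE and the 1-week correlations as they are, because the same-visit answer already comes before the endpoint.

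The cost is analysis programming and a short amendment to the text of 14.7. All the data are already collected, and no visit, questionnaire or subject is added.
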